2.1.1 Primary Immunogenicity Objectives

1. To demonstrate that vaccination with QIVc elicits an immune response that is not inferior to that of an US-licensed QIV containing the recommended strains for the season, in subjects 6 months through 47 months of age, as measured by hemagglutination inhibition (HAI) assay for A/H1N1, B/Yamagata and B/Victoria strains and by microneutralization (MN) assay for A/H3N2 strain, using cell-derived target viruses.

2.1.2 Secondary Immunogenicity Objectives

1. To describe the immunogenicity of QIVc and US-licensed QIV by HAI assay for A/H1N1, B/Victoria, and B/Yamagata strains, and by MN assay for A/H3N2 strain, using egg-derived target viruses.
2. To describe the immunogenicity of QIVc and US-licensed QIV by HAI assay for A/H1N1, B/Victoria, and B/Yamagata strains, and by MN assay for A/H3N2 strain, using cell-derived target viruses.
3. To describe the immunogenicity of QIVc and US-licensed QIV by MN assay for A/H1N1, B/Victoria, and B/Yamagata, in a subset of subjects

2.1.3 Secondary Safety Objectives

1. To evaluate the safety and reactogenicity of QIVc and US-licensed QIV

2.1.4 Exploratory Immunogenicity Objective

1. To evaluate the homologous cell-mediated immunity (CMI) response, pre-vaccination and post-vaccination, in a small population of subjects.
2. To further describe the immune response to vaccination, additional immunogenicity analyses may be conducted such as HAI assay for A/H3N2 using cell- and egg-derived target virus.

2.2 Overall Study Design

This multicenter, phase 3 clinical study evaluates the immunogenicity and safety of a cell-based Quadrivalent subunit influenza virus-vaccine (QIVc) compared to US-licensed QIV in children 6 months through 47 months of age. Study features an observer blind, comparator-controlled design and 2:1 randomization between QIVc and US-licensed QIV.

Subjects who meet the eligibility criteria will be enrolled into the study and randomized to one of the two treatment groups using a 2:1 allocation ratio to receive either Seqirus QIVc or US-licensed QIV.

The study has a treatment period and a follow-up period.

Subjects with a previous influenza vaccination history:

- The treatment period begins at the time of vaccination and ends 28 days after vaccination and will consist of 2 clinical visits and one reminder call to complete the Subject Diary Card.
- The follow up period begins 28 days after vaccination and ends at the time of study completion visit.

Subjects without or unknown previous influenza vaccination history:

- The treatment period begins at the time of first vaccination and ends 28 days after the second vaccination and will consist of 3 clinical visits and two reminder calls to complete the Subject diary card, one after each vaccination.
- The follow-up period begins 28 days after second vaccination and ends at the time of study completion visit.

All subjects, irrespective of previous influenza vaccination history, will receive 1 safety assessment call 90 days after last vaccination during the follow up period and the follow-up period will conclude with a study completion visit (call).

Currently available influenza vaccines are not licensed below age of 6 months, and protocol will exclude any subjects who have received influenza vaccine in the past 6 months. Therefore, all eligible subjects below 12 months of age will be considered as not previously influenza vaccinated for enrolment in the study.

The timing and frequency of the study visits are described in Schedule of Assessments ([Appendix A](#)).

The treatment arms of Study Vaccine comprise:

Study treatment:

Seqirus' Quadrivalent (QIVc): Flucelvax Quadrivalent

The dose to be administered 0.5 mL of QIVc (cell-derived seasonal Quadrivalent influenza vaccine) contains nominally 15 µg of hemagglutinin (HA) of each of the 2 influenza type A strains and each of the 2 influenza type B strains for a total of 60 µg of HA in the vaccine. The strain composition will be that recommended by the World Health Organization (WHO) for Quadrivalent influenza vaccines contemporaneous to the timing of the study.

Comparator treatment:

US-licensed Quadrivalent: Afluria® Quadrivalent

Afluria® Quadrivalent is an inactivated influenza virus vaccine for intramuscular injection. Afluria® Quadrivalent is supplied in a 0.25 mL and a 0.5 mL pre-filled syringe (PFS). For children 6 months through 35 months of age, 0.25 mL dose of vaccine will be administered. For children 36 months through 47 months of age, 0.5 mL will be administered.

Withdrawn Subjects

Subjects may withdraw from the study at any time at their own request or request of the parent or legally acceptable representative (LAR) or they may be withdrawn at

Statistical Analysis Plan

Sponsor Name: Seqirus
Sponsor Protocol ID: V130_10

any time at the discretion of the investigator or Seqirus for safety or administrative reasons.

The reasons for premature withdrawal from the study include the following:

- Adverse event (AE)
- Death
- Withdrawal of consent
- Loss to follow-up
- Other
- Protocol deviation
- Study terminated by Sponsor

In accordance with International Conference on Harmonization (ICH) principles of Good Clinical Practice (GCP) the investigator always has the option to advise a subject to withdraw from the study if the subject's safety or wellbeing is compromised by his or her further participation in the study. Concern for the interests of the subject must always prevail over the interests of the study.

If a subject is withdrawn from the study or further participation is declined, they will continue to have access to medical care and will be treated as per routine medical practice.

Randomization

Enrolled subjects will be randomized in the Interactive Response Technology (IRT) system by a 2:1 ratio and automatically assigned a unique Subject ID. Subjects participating in the CMI subset (approximately 84 subjects) will be enrolled in a limited number of sites through sequential allocation. The Subject ID will be the subject's unique identification number for all eCRFs and associated study documentation that will be used for duration of the study. After randomization, the Screening Number ceases to be used and remains in the Screening and Enrolment Log only. The list of randomization assignments is produced by the EDC/IRT service provider and approved by Seqirus according to applicable Seqirus Standard Operating Procedure (SOP).

Stratification through IRT will be used to ensure a balanced distribution among the age groups, at least 30% of the subjects should be 6 through 23 months and at least 30% of the subjects should be from 24 through 47 months of age.

For A/H1N1, B/Victoria, and B/Yamagata strains, immunogenicity of QIVc and US-licensed QIV will be evaluated by MN assay in a 20% subset of subjects. After blood specimens have been collected a randomly selected subset (20%) of these samples will be analyzed.

If for any reason, after signing the Informed Consent Form (ICF), the subject who is eligible and enrolled fails to be randomized, this is called a randomization failure. The reason for all randomization failures will be recorded in the Screening and Enrollment Log.

If for any reason, after randomization the subject fails to undergo treatment, this is an Early Termination and the reason should be recorded in source document.

The information on these Early Termination subjects should be kept distinct in the source documentation from randomization failures.

Blinding

The trial is designed as an observer-blind study. During the treatment period of the study designated and trained unblinded nurse(s), physician(s), or other qualified health care professional will be responsible for administering the study vaccines to the subjects. They will be instructed not to reveal the identity of the study vaccines either to the subject's parent(s)/LAR/delegate or to the investigative site personnel (i.e., investigator and study nurse) involved in the monitoring of conduct of the trial, except in an emergency if unblinding in IRT is not possible. Vaccine administration should be shielded from the subject's parent(s)/LAR(s) and blinded study personnel. The unblinded personnel should not be involved in data collection or data review such as safety assessments and/or collect study data after the vaccinations. Study vaccines will be assigned through an Interactive Response technology system.

Except in the case of medical necessity, a subject's treatment should not be unblinded without the approval of the Sponsor. In such instance, every effort should be made to contact the Sponsor prior to unblinding. If unblinding occurs, by either accidental unblinding or emergency unblinding for a serious adverse event, prior to completion of the study, the investigator must promptly contact the Sponsor and document the circumstances on appropriate forms. In case of an emergency, the information can be retrieved by the Investigator from the IRT system either via web or phone (a 24/7 backup service). If the subject unblinded by the Investigator, the subject could be removed from an Analysis Set.

Investigators, Seqirus study team members, and all External Service Providers (ESPs) who are directly involved in the conduct of the trial or in the analysis of the study results, or have contact with study centers, will remain blinded to the treatment codes until the final database lock at the end of the study. Only biostatisticians conducting the statistical analysis for the treatment period, will have access to the individual treatment codes. No unblinded individual subject level information will be shared with Seqirus and ESP personnel conducting the study until the final database lock. Seqirus study team members preparing the draft CSR with treatment period data will remain blinded to the individual treatment codes.

If a subject is unblinded during the study, it is to be reported as major Protocol Deviation (PD), except for subjects unblinded by Pharmacovigilance due to suspected unexpected serious adverse reactions (SUSAR). The unblinding will be documented appropriately. The unblinded subject(s) are excluded from the Per Protocol Set (PPS).

Planned Unblinding procedures

The relevant portions of the clinical database will be cleaned and locked after collection of safety and immunogenicity data has been completed for all subjects during the treatment period of the study, i.e. up to 28 days following the last vaccination dose (final treatment period data). Only personnel of the ESP and Seqirus conducting the statistical analysis will have access to the individual treatment codes. This information will not be shared with Seqirus and ESP personnel conducting the study until the follow up safety data has been locked for final analysis. Seqirus study

team members preparing the CSR with treatment period data will remain blinded to the individual treatment codes. The results will not be shared with investigators and other site staff.

Safety follow up data will be locked when all subjects have completed all clinical data collected up to 180 days following the last vaccination dose (end of study). The Seqirus Benefit Risk Physician responsible for Sponsor's assessment of adverse events during the follow up phase will remain blinded at individual and group level through the follow up period, until final database lock at study completion. A final clinical study report will present all clinical study data collected up to 180 days following the last vaccination dose, including safety follow up data.

2.3 Sample Size and Power

Seqirus QIVc will be tested against comparator, i.e. US-licensed comparator QIV. The treatment randomization ratio is 2:1 (Seqirus QIVc: Comparator QIV).

This study is designed to achieve at least 90% power to demonstrate noninferiority for all of the 8 endpoints: seroconversion rates for 4 strains and Geometric Mean Titers (GMTs) for 4 strains using a one-sided alpha of 0.025 for each comparison. No alpha adjustment for multiple endpoints will be made. For comparisons of Seroconversion rate (SCR) a noninferiority margin of 10% (Comparator QIV-Seqirus QIVc) will be employed. It is assumed that the SCRs for A/H1N1, B strains and A/H3N2 based on Cell-based Trivalent Influenza Vaccine (TIVc) are 81%, 69% and 85% respectively. These estimates are based on the estimated SCR rates of historical data, namely from study *V58P16*.

It is also assumed that the expected difference between antibody titers (QIV minus QIVc) is consistent with the SCR differences reported as per *V58P16*, namely 7% for A/H1N1 and 5% for A/H3N2 (based on the MN assay).

It is assumed that there is no difference between Seqirus QIVc and the comparator QIV for the B/strain.

For comparison of GMT ratio, a noninferiority margin of 1.5 (Comparator QIV/ Seqirus QIVc, equivalent to a difference on the log scale of 0.405465108) will be employed for the assessment for the A/H1N1, A/H3N2 and B strains. It is assumed that the GMT ratios for A/H1N1, A/H3N2 and B strains for QIVc are 1.49 for the A/H1N1, 1.00 for the A/H3N2 (based on the MN assay) and 0.84 for the B-strains. These GMT ratio estimates are consistent to those observed from protocol *V58P16*. It is assumed that the standard deviation of $\log_e(\text{titer})$ is 1.3 across all strains.

Under these assumptions and with n evaluable = 1450 in the Seqirus QIVc group and 725 in the Comparator QIV the power for 4 GMT ratio endpoints is 94.90% and the power for 4 SCR endpoints is 99.40%. The overall global power of the 8 endpoints is then $94.9\% \times 99.4\% = 94.33\%$.

This provides a total N evaluable = 2175. Allowing for a 10% drop-out, 2418 subjects will be recruited for immunogenicity assessment. Approximately 84 additional subjects between 24 through 47 months of age will be enrolled to study CMI

Statistical Analysis Plan

Sponsor Name: Seqirus
Sponsor Protocol ID: V130_10

response, in order to have approximately 50 and 25 evaluable subjects in the QIVc and Comparator QIV groups, respectively. Thus, approximately 2502 subjects will be enrolled into study.

Sample size calculations were performed using PASS v12.0.02.

Table 2.3-1 Summarize the list of all co-primary endpoints with strains, the planned noninferiority margin and the underlying assumptions used for the sample size computations.

Table 2.3-1: Summary of Assumptions Used for Sample Size Calculations

NI Comparison	A/H1N1	A/H3N2	B strains
Test significance level, alpha (1-sided)	2.50%	2.50%	2.50%
Noninferiority Margin for the SCR comparison (%)	10	10	10
Assumed true SCR	81%	85%	69%
Power for SCR comparison tests for each strain (%)	100%	100%	99.7%
Global Power for 4 SCR endpoints	99.40%		
Noninferiority Margin for the GMT ratio	1.5	1.5	1.5
Common Standard Deviation of $\log_e(\text{titer})$	1.3	1.3	1.3
Power for GMT ratio tests for each strain (%)	100%	100%	97.42%
Global Power for 4 GMT ratio Endpoints	94.90%		
Global Power for 8 co-primary Endpoints	94.33%		

3. Immunogenicity and Safety Variables

3.1 Co-Primary Immunogenicity Endpoints

Serum HAI antibody titer against A/H1N1, B/Victoria and B/Yamagata vaccine strains at Day 29/57, using cell-derived target virus:

- GMT by HAI assay
- SCR defined as the percentage of subjects with either a pre-vaccination HAI titer < 1:10 and a post-vaccination HAI titer \geq 1:40, or a pre vaccination HAI titer \geq 1:10 and a \geq 4-fold increase in post vaccination HAI titer

Serum neutralizing antibody titer against A/H3N2 vaccine strain at Day 29/57, using cell-derived target virus:

- GMT by MN assay
- SCR defined as the percentage of subjects with either a pre-vaccination MN titer < 1:10 and a post-vaccination MN titer \geq 1:40, or a pre vaccination MN titer \geq 1:10 and a \geq 4-fold increase in post vaccination MN titer

Derived Variables:

- The GMT ratio (QIV/QIVc) for each strain
- The inter-group difference in the SCRs (QIV minus QIVc) for each strain

The noninferiority of QIVc compared to US-licensed QIV will be assessed for the eight co-primary endpoints of GMT and SCR for each cell-derived target virus strain included in QIVc as follows:

- The GMT ratio for the A/H1N1 strain (HAI assay)
- The GMT ratio for the A/H3N2 strain (MN assay)
- The GMT ratio for the B Yamagata strain (HAI assay)
- The GMT ratio for the B Victoria strain (HAI assay)
- The difference between the SCRs for the A/H1N1 strain (HAI assay)
- The difference between the SCRs for the A/H3N2 strain (MN assay)
- The difference between the SCRs for the B Yamagata strain (HAI assay)
- The difference between the SCRs for the B Victoria strain (HAI assay)

3.2 Secondary Endpoints

3.2.1 Secondary Safety Endpoints

The measures for assessing safety and reactogenicity are as follows:

- Percentage of subjects with solicited AEs will be assessed for 7 days after each study vaccination
- Percentage of subjects with any unsolicited AEs from Day 1 to Day 29 (in previously vaccinated subjects) and from Day 1 to Day 57 (in not previously vaccinated subjects)
- Percentage of subjects with any Serious Adverse Events (SAEs), New Onset of Chronic Diseases (NOCDs), AEs leading to withdrawal from during the entire study period (i.e., from Day 1 to Day 181 for Previously vaccinated subjects or from Day 1 to Day 209 for not previously vaccinated subjects).

3.2.2 Secondary Immunogenicity Endpoints

Humoral immune response in term of HAI antibodies against A/H1N1, B/Victoria and B/Yamagata strains, using cell- and egg- derived target virus:

- GMT by HAI assay at Days 1 and 29/57
- Geometric Mean Ratio (GMR), defined as the fold increase in serum HAI GMT post vaccination (Day 29/57) compared to prevaccination (Day 1)
- Seropositivity rates (percentages of subjects with HAI titer \geq 1:10) at Days 1 and 29/57
- Percentages of subjects with HAI titer \geq 1:40 at Days 1 and 29/57
- SCR by HAI assay

Neutralizing antibody titers against A/H3N2 vaccine strains, using cell- and egg-derived target virus:

- GMT by MN assay at Days 1 and 29/57
- Geometric Mean Ratio (GMR), defined as the fold increase in serum MN GMT post vaccination (Day 29/57) compared to prevaccination (Day 1)
- Seropositivity rates (percentages of subjects with MN titer \geq 1:10) at Days 1 and 29/57

- SCR by MN assay, where SCR for MN is defined as the percentage of subjects with either a prevaccination MN titer < 1: 10 and a post vaccination MN titer \geq 1:40, or a prevaccination MN titer \geq 1: 10 (LLOQ) and a \geq 4-fold increase in post vaccination MN titer

Neutralizing antibody titers against A/H1N1, B/Victoria and B/Yamagata vaccine strains, in a subset of subjects:

- GMT by MN assay at Days 1 and 29/57
- GMR, defined as the fold increase in serum MN GMT post vaccination (Day 29/57) compared to prevaccination (Day 1)
- Seropositivity rates (percentages of subjects with MN titer \geq 1:10(Lower Limit of Quantification (LLOQ))) at Days 1 and 29/57
- SCR by MN assay

3.3 Exploratory Immunogenicity Endpoints

The CMI responses to vaccination are considered exploratory endpoints in the study. CD4+ T-cell / CD8+ T-cell responses to antigen stimulation in vitro will be indicated by expression of activation markers (CD154, IL2, IL13, IFN γ , and TNF α), as measured by immunostaining and flow cytometry at baseline (day 1) and Day 29 (previously vaccinated subjects) or at baseline (Day 1) and Day 57 (not previously vaccinated subjects), in approximately 84 subjects (2:1 ratio, 56 subjects in QIVc and 28 subjects in licensed QIV group).

4. Analysis populations

There will be five analysis populations defined for the study analyses:

4.1 All Enrolled Set

All screened subjects who provide informed consent, receive subject ID, and provide demographic and/or baseline screening information, regardless of the subject's randomization and treatment status in the study.

4.2 Full Analysis Set (FAS)

All subjects in the All Enrolled Set who are randomized and receive a study vaccination. The FAS will be used to produce summaries and listings of subject characteristics.

In case of misrandomization with regard to treatment arm, subjects in the FAS will be analyzed "as randomized" (i.e., according to the vaccine a subject was designated to receive, which may be different from the vaccine the subject actually received).

4.3 Safety Set

Overall Safety Set

All subjects who are in the solicited safety set and/or in the unsolicited safety set. In case of vaccination error, subjects will be analyzed as “treated” (i.e., according to the vaccine a subject receives, rather than the vaccine to which the subject is randomized).

If a subject received the correct study vaccine (dose, batch) but from another ongoing study at the site then the subject’s safety data should be included in the safety analysis.

If a subject is unblinded during the study, he/she will be included in all safety sets. The Overall Safety Set will be used to produce summaries and listings of all overall and unsolicited safety data after any vaccination. Subjects will be analysed according to the treatment they received.

Solicited Safety Set

All subjects in the Exposed Set with any solicited AE data.

Unsolicited Safety Set

All subjects in the Exposed Set with unsolicited AE data.

4.4 Full Analysis Set – Immunogenicity

The FAS for immunogenicity analyses will comprise all subjects in the FAS who:

- receive vaccine on Day 1
- provide serology specimens which yield valid serology assay results from both Day 1 and Day 29 (Previously vaccinated subjects) or Day 1 and Day 57 (Not previously vaccinated subjects)

The FAS will be used to produce summaries and listings of subject characteristics.

In case of vaccination error, subjects in the FAS Immunogenicity will be analyzed “as randomized” (i.e., according to the vaccine a subject was designated to receive, which may be different from the vaccine the subject actually received).

If a subject is unblinded during the study, he/she will be included in the FAS Immunogenicity.

4.5 Per Protocol Set (PPS)

The PPS will comprise all subjects in the FAS Immunogenicity who do not have any protocol deviations that are medically assessed as potentially impacting on immunogenicity results.

The PPS will be the primary set of interest for the primary/secondary immunogenicity analysis and a supporting analysis will be performed using the FAS Immunogenicity. Membership of the PPS will be determined prior to unblinding the study.

Duplicate tables of primary and secondary immunogenicity analyses may also be produced based on the FAS Immunogenicity population if there is >5% difference in the total number of subjects between the Per-Protocol Population and the FAS Immunogenicity Population. The decision to produce tables based on the FAS Immunogenicity Population will be made by Seqirus after population sets are finalized and prior to unblinding.

Examples for subjects excluded due to other reasons than protocol deviations are subjects who withdrew informed consent.

In case of misrandomization with regard to treatment arm, the subject is excluded from the PPS.

If a subject is unblinded during the study, except for SUSAR, he/she will be excluded from the PPS.

If the serum sample was collected outside the time window of 21 days, the subject did not comply with the blood draw schedule and will be excluded from the PPS population. Hence, subjects will be excluded from PPS if blood draws >21 days after any vaccination.

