Subjects will provide a serological specimen via a blood draw before vaccination on Day 1 and 28 days after last vaccination. Previously vaccinated subjects will provide a serological specimen on Day 1 and Day 29 (vaccination on Day 1), while not previously vaccinated subjects will provide a serological specimen on Day 1 and Day 57 (vaccination at Day 1 and Day 29). The serological specimen on the day of vaccination will be obtained before vaccination. For the majority of subjects (approximately 2418), immunogenicity will be measured by HAI and MN assays from the serological specimen. In a small group of approximately 84 subjects, evaluation of CMI response will be performed instead of the immunogenicity evaluation.

Currently available influenza vaccines are not licensed below the age of 6 months. This protocol will exclude any subjects who have received influenza vaccine in the past 6 months. Therefore, all eligible subjects below 12 months of age will be considered as not previously vaccinated against influenza for study enrollment.

The final analysis of the primary and secondary immunogenicity endpoints will be conducted on cleaned and locked data once all subjects have completed all immunogenicity assessments (end of treatment period, i.e. up to 28 days following the last vaccination dose). At this time, the analysis of all solicited adverse events and of unsolicited adverse events reported during the treatment period will also be conducted. These results will be used to prepare a Clinical Study Report (CSR) with treatment period data. No individual unblinded listings will be generated at this stage. A final CSR will present all clinical study data collected up to 180 days following the last vaccination dose, including safety data collected during the follow up period.

Details of the study procedures and assessments are provided in [Section 5, Study Procedures](#) and [Section 7, Assessments](#), respectively.

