4.5.1 Important Protocol Deviations Leading to Exclusion from the PPS Analysis

A protocol deviation (PD) is any change, divergence, or departure from the study design or procedures of a study protocol. A protocol deviation may be a reason to remove data from an analysis set at the time of analysis. PDs can be either observable or programmable. Programmable PDs are those PDs that can be programmed from the data recorded in the clinical database. Observable PDs are PDs identified by CRAs or other team members.

PDs will be classified as major and minor using a prespecified list of types of deviations. Major PDs are defined in accordance with ICH E3 as important PDs related to study inclusion or exclusion criteria, conduct of the trial, subject management or subject assessment resulting in the potential to jeopardize the safety or rights of the trial subjects or the scientific value of the trial.

All PDs will be evaluated before unblinding and most will be classified into the following categories:

- Subject randomized and did not satisfy entry criteria
- Subject received the wrong treatment or incorrect dose
- Subject took an excluded concomitant medication
- Key study procedures missed or performed out of window, such as, for immunogenicity if the serum sample was collected outside the time window of 21 days the subject did not comply with the blood draw schedule and will be excluded from the PPS population. Hence, subjects will be excluded from PPS if blood draws >21 days after any vaccination.

The impact of major PDs on the efficacy, immunogenicity and/or safety results will be investigated by assessing the robustness of the study results.

Major PDs will lead to exclusion of the subject or part of the subject's data from at least one analysis set.

The number of subjects in any and by PD category will be summarized by treatment group, center and overall. Individual subject listings will be provided in an appendix, sorted by subject and by PD category.

Prior to unblinding the analysis, designated Seqirus staff will develop a memo that describes the PDs that led to exclusions from analysis sets. This memo will be signed off by at least the Biostatistician and the Clinical Scientist and will be included in the trial master file (Exclusion Memo).

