5.1 Time points and Visit Windows

A summary of the assessments required at each study visit is described in [\(Appendix A\)](#).

Day 1 is defined as the day of first dose of the vaccination.

Relative days after Day 1 are calculated as (assessment date – Day 1 date) + 1. Relative days prior to Day 1 are calculated as (assessment date – Day 1 date). The day prior to Day 1 is Day -1

The following visit windows will be used.

Table 5.1-1: Visit windows for previously vaccinated subjects

Statistical Analysis Plan

Sponsor Name: Seqirus
Sponsor Protocol ID: V130_10

Study part	Scheduled visit	Time interval (days)
Screening	Screening Visit	< 10 Days before Day 1
Treatment period	Clinic Visit V1	Day 1
	Reminder Phone V1	Day 3 (-1/+1 Day)
	Clinic Visit V2	Day 28 (+ 7 Days)
Follow-up Period	Safety Phone call V3	Day 90 (+ 7 Days)
	Safety Phone call V4	Day 180 (+ 14 Days)

Table 5.1-2: Visit windows for not previously vaccinated subjects

Study part	Scheduled visit	Time interval (days)
Screening	Screening Visit	< 10 Days before Day 1
Treatment period	Clinic Visit V1	Day 1
	Reminder Phone V1	Day 3 (-1/+1 Day)
	Clinic Visit V2	Day 28 (+ 7 Days)
	Reminder Phone	V2 + 2 Days (-1/+1 Day)
	Clinic Visit V3	V2 + 28 Days (+7 Days)
Follow-up Period	Safety Phone call V4	V2 + 90 Days (+7 Days)
	Safety Phone call V5	V2 + 180 Days (+14 Days)

Visit window deviations will be reviewed prior to unblinding.

5.2 Missing Values – Missing Visit.

Missing, unused and spurious data will be dealt with as such. There is no intention to implement any procedure for replacing missing data.

Titer values recorded as <1:10 (or < lower limit of quantification [LLOQ]) will be summarized as 1:5 (or ½* LLOQ).

No imputation of missing solicited or unsolicited AEs will be used but implausible measurement will be removed as described below. The percentage of subjects with missing solicited AE assessments (e.g. missing Patient Diary) and missing Safety Phone Calls or Safety Assessments will be reported for each time period.

Missing immunogenicity values are considered missing completely at random (MCAR) and therefore will not contain information that impact the result of the analysis (i.e., not informative). Imputation methods will therefore not be used.

The PPS will be used for the primary immunogenicity analysis and a supporting analysis will be performed using the FAS Immunogenicity, as noted in Section 4.4 FAS Immunogenicity.

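### As worded, the 21-day blood-draw rule in SAP 4.5 and 4.5.1 excludes every child sampled on schedule from the Per Protocol Set, and no usable exclusion limit is given in its place

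*SAP*

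**What the plan says.** **The exclusion rule.** SAP 4.5 ends its definition of the PPS with "Hence, subjects will be excluded from PPS if blood draws >21 days after any vaccination". SAP 4.5.1 repeats it in the list of deviation categories, under the item "Key study procedures missed or performed out of window". The lead-in there is "if the serum sample was collected outside the time window of 21 days the subject did not comply with the blood draw schedule", and 4.5 has an equivalent sentence.

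**The sampling schedule.** Protocol 3.1 states: "Subjects will provide a serological specimen via a blood draw before vaccination on Day 1 and 28 days after last vaccination". Protocol Tables 1-1 and 1-2, SAP Tables 5.1-1 and 5.1-2 and SAP Appendix A place the post-vaccination visit 28 days after the last dose, with a window of 0 to +7 days. That is V2 for one-dose children and V3 for two-dose children. Two-dose children have no draw at the Day 29 visit.

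**The parent set.** Under SAP 4.4, children in the Full Analysis Set – Immunogenicity must "provide serology specimens which yield valid serology assay results from both Day 1 and Day 29" (Day 57 for two-dose children). The PPS is a subset of these children.

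**The role of the PPS.** SAP 6.5.1.2 makes it the set for the primary immunogenicity analysis. SAP 6.5.1.1 requires all eight co-primary endpoints to succeed.

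**The concern.** The rule disqualifies the same sample that membership of the parent set requires. Counting from any vaccination adds a second fault: in a two-dose child the interval from the first dose must also be 21 days or less, although the sample is taken about two months after that dose.

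The lead-in does not resolve this. A time window of 21 days could be a minimum interval, a tolerance on either side of the visit, or a tolerance after it. The text gives no reference date, direction or limits.

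The rest of the plan does not supply them:

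- Protocol 8.3.5, which defines the PPS, has no 21-day rule.
- The 0 to +7 day visit window governs scheduling. Nothing says that missing it removes a child from the PPS.
- Appendix A presents itself as binding where the protocol is inconsistent, but sets no PPS limit.
- SAP section 7 records only the renaming of the evaluable set.

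What is at stake is prespecification of the primary analysis set. SAP 4.5.1 provides for deviations found by program: "Programmable PDs are those PDs that can be programmed from the data recorded in the clinical database". A rule on draw dates is naturally of that kind, although the SAP does not say so for this one. Coded as written, it empties the set. Any other coding uses limits that the SAP does not contain, chosen when the draw dates are already known.

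**Working it through.** **1. Interval from vaccination to draw**

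Inputs: visit at +28 days, window 0 to +7 (protocol Tables 1-1 and 1-2; SAP 5.1 and Appendix A); limit 21 days (SAP 4.5 and 4.5.1).

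| Children | Counted from | Scheduled draw (days) | Days past 21 |
|---|---|---|---|
| One dose | the only dose | 28+0 to 28+7 = 28–35 | 7–14 |
| Two doses | dose 2 | 28+0 to 28+7 = 28–35 | 7–14 |
| Two doses | dose 1 | (28 to 35) + (28 to 35) = 56–70 | 35–49 |

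No scheduled draw falls at 21 days or less from any dose. If all 2175 planned evaluable children (SAP 2.3) are drawn on schedule, the literal PPS has 0 members.

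**2. Plausible intended readings, counted from the last dose**

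| Reading | Interval kept (days) | Contains 28–35? | Draw on day 25 |
|---|---|---|---|
| At least 21 days | 21 or more | yes | kept |
| Visit ± 21 days | 28−21 to 28+21 = 7–49 | yes | kept |
| Visit to 21 days later | 28 to 28+21 = 28–49 | yes | excluded |

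Each reading keeps every on-schedule child. They differ for off-window draws. The day-25 draw is one example. A draw after day 49 is another: the first reading keeps it and the other two exclude it.

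**3. The plan's own power figure**

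Inputs from SAP 2.3: 1450 and 725 evaluable, one-sided alpha 0.025, margins 1.5 (GMT ratio) and 10% (SCR), SD of log titer 1.3, B-strain QIVc/QIV GMT ratio 0.84, B-strain SCR 69% in both arms. The A-strain tests are taken as 100%, as in SAP Table 2.3-1. Normal approximation:

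- B-strain GMT: SE = 1.3 × √(1/1450 + 1/725) = 0.0591. Power = Φ((ln 1.5 + ln 0.84)/0.0591 − 1.96) = 97.43% (plan: 97.42%).
- B-strain SCR: SE = √(0.69 × 0.31 × (1/1450 + 1/725)) = 0.0210. Power = Φ(0.10/0.0210 − 1.96) = 99.74% (plan: 99.7%).
- All eight endpoints: 0.9743² × 0.9974² = 94.4% (plan: 94.33%).

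The plan's figure is reproduced and is not in question.

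**4. Effect of off-window exclusions**

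The documents give no number of off-window draws, so these shares are assumptions. They are taken as lost in 2:1 proportion, beyond the 10% drop-out allowance.

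| Share of 2175 excluded | Global power |
|---|---|
| 0% | 94.4% |
| 1% | 94.2% |
| 5% | 93.0% |
| 10% | 91.1% |

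At 273 exclusions (273/2175 = 12.6%, N = 1902) power is 90.02%, about the 90% design target. At 276 exclusions (N = 1899) it is 89.95%.

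**The case against.** The best defence is that nobody would apply the sentence literally. The lead-in ties exclusion to not keeping the blood-draw schedule, and a child sampled at Day 29 or Day 57 has kept it. SAP 4.4 requires that sample, and Appendix A describes itself as the master representation of the trial.

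There are also procedural safeguards. The SAP says "Membership of the PPS will be determined prior to unblinding the study" and "Visit window deviations will be reviewed prior to unblinding". It adds a prespecified list of deviation types, sponsor review of the deviation listings, and an exclusion memo signed before unblinding by at least the biostatistician and the clinical scientist. A supporting analysis on the Full Analysis Set – Immunogenicity has no 21-day rule in its definition. The Protocol Deviation Specifications named in protocol 8.3.7 are not among the documents reviewed and may contain proper limits.

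Much of this stands. An empty PPS is unlikely to reach analysis, blinded decisions limit bias, and the power range in step 4 describes PPS losses from any cause. The criticism is therefore confined to the SAP wording.

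The defence does not remove the fault. Blinded review needs a rule to apply, and the only one the SAP states is wrong. The sentence appears in two sections and is introduced as the consequence of the lead-in, so it cannot simply be set aside. A supporting set does not replace the primary one.

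**Conclusion.** The concern holds. As written, the rule contradicts the sampling schedule and, on full schedule compliance, leaves 0 of 2175 planned evaluable children in the primary set. That is almost certainly not the intention.

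The practical gap is narrower: the SAP does not say which early or late draws remove a child from the PPS. Under the three plausible readings, on-schedule children and the stated 94.33% power are untouched. The effect of off-window draws cannot be sized from the documents. On the assumed losses of 1% to 10%, power would be about 94.2% to 91.1%, still above the 90% target.

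The reason to require a change is that a stated rule defining the primary set for all eight tests gives a wrong result and cannot be executed as intended. It is not a predicted loss of power.

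**What to change.** Before unblinding, replace the sentence and its lead-in, in both SAP 4.5 and SAP 4.5.1, with a single blood-draw window that:

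- is counted from the last vaccination, not from any vaccination;
- has an explicit lower and upper limit in days, chosen by the sponsor;
- contains the scheduled 28 to 35 days.

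Check the window against SAP Appendix A and the Protocol Deviation Specifications so that all three agree, and record the change in SAP section 7. The cost is SAP wording only. No visit, sample or trial procedure changes.
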